11 DESCRIPTION OF STUDY TREATMENTS

11.1 Description of Investigational Product(s)

The chemical name of GED-0507-34-Levo (GED0507) is (S)-(-)-3-(4-aminophenyl))-2-methoxypropionic acid.

GED-0507-34-Levo will be provided as 80 mg tablets. Placebo will be provided as identically appearing tablets.

11.2 Treatment Administration and Schedule

Tablets will be taken by mouth BID, in the morning (AM) and in the evening (PM), approximately 12 hours apart, on an empty stomach (ie, at least 3 hours after eating and at least 1 hour prior to eating breakfast or dinner).

80 mg BID group: 2 tablets AM (1 placebo + 1 active 80 mg) and 2 tablets PM

(1 placebo + 1 active 80 mg).

160 mg BID group: 2 tablets AM (2 active 80 mg) and 2 tablets PM (2 active 80 mg).

Placebo Group: 2 tablets AM and 2 tablets PM.

11.3 Method of Treatment Assignment

After the ICF is signed, subjects will be assigned a subject identification number using a centralized IVRS/IWRS. At the Baseline Visit, a centralized schema will be applied to assign subjects who meet the inclusion/exclusion criteria in a 1:1:1 ratio to receive GED-0507-34-Levo 80 mg by mouth (PO) BID, 160 mg PO BID, or placebo.

Designated study personnel at the investigational sites will be assigned password-protected, coded identification numbers that give them authorization to connect to IWRS to randomize subjects. The system will present a menu of questions by which the study personnel will identify the subject and confirm eligibility. When all questions have been answered, the IWRS will assign a randomization identification number.

During the study visits, the pharmacy or authorized study personnel at the investigational site will dispense coded IP kits in accordance with the randomization number assigned by the IWRS.

11.4 Packaging and Labeling

All IP, including placebo and GED-0507-34-Levo tablets, will be supplied by PPM SERVICES SA (or designee) to the principal Investigator as HDPE bottles during the Double-blind Placebo-controlled Phase.

GED-0507-34-Levo will be provided in HDPE bottles as 80 mg tablets.. Tablets will be taken by mouth BID, morning and evening, approximately 12 hours apart, on an empty stomach (ie, at least 3 hours after eating and at least 1 hour prior to eating breakfast or dinner).

The label(s) for IP will include the protocol number, IP name, dosage form and strength (where applicable), amount of IP per container, lot number, expiry date (where applicable), medication identification/kit number, dosing instructions, storage conditions, and required caution statements and/or regulatory statements as applicable. Additional information may be included on the label as applicable per local regulations.

11.5 Investigational Product Accountability and Disposal

The Investigator, or designee, is responsible for taking an inventory of each shipment of IP received and comparing it with the accompanying IP shipping order/packing list.

The Investigator, or designee, will verify the accuracy of the information on the form, sign and date it, retain a copy in the study file, and return a copy to PPM SERVICES SA.

The IP will be stored according to the storage conditions identified on the drug label. At the study site, all IP will be stored in a locked, safe area to prevent unauthorized access.

PPM SERVICES SA (or designee) will review with the Investigator and relevant site personnel the process for IP return, disposal, and/or destruction, including responsibilities for the site versus PPM SERVICES SA (or designee).

11.6 Investigational Product Compliance

Study personnel will review the instructions printed on the package with the study subjects prior to dispensing the IP. Investigational Product will be dispensed as noted in Table 1 Schedule of Events. The subjects will be instructed to return the IP containers, including any unused medication, to the study site at each visit for tablet counts and reconciliation. Subjects will be asked whether they have taken their IP as instructed at each study visit. Any problems with IP compliance will be reviewed with the subject. If a subject misses 4 or more consecutive days of dosing, PPM SERVICES SA must be contacted to decide whether dosing should resume or whether the subject should be terminated from the study.

Gross compliance problems (eg, missing 4 or more consecutive days of dosing or taking less than 75% of the doses between study visits) should be discussed with PPM SERVICES SA. Compliance is defined as taking between 80% and 120% of dispensed IP.

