9.10 Dosing

9.10.1 Investigational Product Dispensing and Counting

After the subject has satisfied all inclusion and exclusion criteria, IP will be dispensed as specified by the IWRS. Subjects must be instructed to return all previously issued empty HDPE bottles and/or unused IP at the time that new IP is issued. A detailed record of tablets issued and returned at each visit must be maintained in the subject's record.

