13.2 Study Population Definitions

Safety analyses will be based on the safety population, which will include all subjects who are randomized and receive at least 1 dose of IP. Subjects will be included in the treatment group corresponding to the IP they actually received for the analyses using the safety population.

The ITT population will consist of all subjects who are randomized as specified in the protocol and receive at least 1 dose of IP. Subjects will be included in the treatment group to which they were randomized, irrespective of the treatment actually received, for the analyses using the ITT population.

The modified intent-to treat (mITT) population is defined as the ITT population with the exclusion of the subjects who: a) withdraw from the study due to a reason clearly documented as independent of either the study treatment or the UC; or b) remained on study for less than 7 days. The mITT population will be the primary population for efficacy analyses.

The PP population will consist of all subjects included in the mITT population who have at least 1 post-baseline efficacy evaluation and no protocol violations that may substantially affect the efficacy results. The final determination on these protocol violations, and thereby the composition of the PP population, will be made prior to the Placebo-controlled Phase analysis and will be separately documented.

The PK population will consist of all subjects in the safety population who have at least one analyzable PK sample. It is expected that the PK population will consist of approximately 50% of the overall study population.

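### Compliance is measured against tablets dispensed, so the 120% limit cannot be reached and fully adherent early leavers can score below 80%

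*Combined protocol and SAP*

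**What the plan says.** Section 11.6 gives the definition: "Compliance is defined as taking between 80% and 120% of dispensed IP". The sentence just before it works on another base. Among the compliance problems to be raised with the sponsor it lists "taking less than 75% of the doses between study visits", which refers to scheduled doses and not to tablets supplied.

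The counts come from two places. Section 9.10.1 says: "A detailed record of tablets issued and returned at each visit must be maintained in the subject's record". Section 11.6 has subjects "return the IP containers, including any unused medication, to the study site at each visit for tablet counts and reconciliation".

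Every arm takes four tablets a day; Section 11.2 has, for instance, "Placebo Group: 2 tablets AM and 2 tablets PM". Table 1 shows drug dispensed at Weeks 0 and 4 only, with visit windows of 3 days either side at Weeks 4 and 8. Tablets are counted at each treatment visit. The Synopsis names the bottle volume, but no section gives the number of tablets per bottle or any overage.

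Section 13.2 restricts the per-protocol population to mITT subjects with a post-baseline efficacy evaluation and "no protocol violations that may substantially affect the efficacy results". It does not mention the 80-120% band, and neither does any other part of Section 13. Section 13.1 leaves the full detail to a separate SAP.

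**The concern.** A ceiling of 120% makes sense against doses due. Against tablets supplied it does nothing, because nobody can use more of a supply than was issued. The same denominator also counts tablets that were issued but never due, so it penalises a subject for leaving before a supply ran out or for receiving a generous pack.

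Early leaving is not a rare or neutral event here. Section 13.3 plans for 15% dropout. Section 5.5 reports that many Phase 2a subjects left within the first 4 weeks for lack of effect or worsening. Section 15 lists lack of effect after at least 4 weeks as a reason for discontinuation, and that is just after the second supply is issued. Section 13.4 counts withdrawals as not in remission.

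If low compliance were used to exclude subjects from the per-protocol set, the subjects excluded would include non-remitters who took every dose, and the remission rates in that set would rise. The Phase 2a results in Section 5.4 show how far the two kinds of population can differ: 14.7% remission overall against 33.3% per protocol. That gap is context only. Nothing in the protocol attributes it to a compliance rule.

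**Working it through.** The band is a definition, so there is no planned figure to reproduce. The check applies it to simple cases.

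**Inputs**
- 4 tablets a day (Section 11.2), so 28 × 4 = 112 due per supply period and 56 × 4 = 224 due in all.
- Supplies issued at Weeks 0 and 4 (Table 1).
- Spare fraction *s*: not stated; assumed range 0 to 50%.
- Cumulative count over all drug issued: an assumption, since Section 11.6 does not say.

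**Step 1: upper limit.** Score = (issued − returned) / issued. Returned cannot be negative, so the score is at most 100%. With 25% spare, a subject who uses a whole 28-day supply has taken 140/112 = 125% of the tablets due but scores 140/140 = 100%.

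**Step 2: early leavers who took every dose, no spare.** Score = 4*d*/112 for leaving on day *d* before the Week 4 supply, and 4*d*/224 after it.

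| Leaving day | Taken | Issued | Score |
|---|---|---|---|
| 14 | 56 | 112 | 50.0% |
| 22 | 88 | 112 | 78.6% |
| 23 | 92 | 112 | 82.1% |
| 27 | 108 | 112 | 96.4% |
| 28 (second supply issued) | 112 | 224 | 50.0% |
| 35 | 140 | 224 | 62.5% |
| 44 | 176 | 224 | 78.6% |
| 45 | 180 | 224 | 80.4% |

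The cut-offs are 0.8 × 112/4 = 22.4 days and 0.8 × 224/4 = 44.8 days. Spare supply multiplies both by (1 + *s*). At 10% spare they become 24.6 and 49.3 days.

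**Step 3: perfect completers.** Score = 1/(1 + *s*): 95.2% at 5% spare, 90.9% at 10%, 83.3% at 20%, 80.0% at 25%, 76.9% at 30% and 66.7% at 50%. The subject fails only when *s* exceeds 1/0.8 − 1 = 25%.

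As an illustration, suppose the packs just cover the visit windows. The first supply must last to Day 31 (31 × 4 = 124). The second must last from Day 25 to Day 59 (34 × 4 = 136). The total is 260. A perfect completer scores 224/260 = 86.2% and passes. The 80% cut, however, now needs 0.8 × 260 = 208 tablets, which is 208/224 = 92.9% of those due. One missed day in the second period scores 220/260 = 84.6% cumulatively (pass) but 108/136 = 79.4% if that supply is scored alone (fail).

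**Step 4: tablets due as the denominator.** The Day 14 leaver scores 56/56 = 100% and the Day 35 leaver 140/140 = 100%. A subject who used all 112 tablets by Day 14 scores 112/56 = 200% and is flagged, against 100% now. The 125% case in Step 1 is flagged too. One limit remains: with 260 tablets issued, a completer who used them all scores 260/224 = 116% and is not flagged. A whole-treatment score can pass 120% for a completer only if spare exceeds 20%.

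**The case against.** The strongest reply is that this is loose wording. A 120% ceiling, next to a sentence about doses between visits, suggests that the authors meant doses due. No analysis in Section 13 uses the band, the primary analysis is on the mITT population, and a separate SAP is foreseen. All of that is true. It limits the consequence but does not repair the definition, which as written gives wrong classifications.

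Several stronger readings are tempting, and the documents do not support them.

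- *Anyone with spare tablets, or anyone leaving early, is classed non-compliant.* Spare supply alone does this to a perfect completer only above 25%, and no pack size is given. With no spare, adherent leavers on Days 23 to 27 or from Day 45 pass.
- *The plan removes adherent subjects from the per-protocol set.* No such rule is written. Section 13.2 leaves the relevant violations to be determined and documented before the analysis.
- *Over-use would go unseen in the trial.* The band would miss it, but other records need not. Section 11.6 also has questioning and the two triggers for gross problems, and Section 14.1 sends overdoses to the drug exposure page. At the Day 7 count, a subject on 6 tablets a day would show 42 gone against 28 due.
- *In the 80 mg BID arm, active and placebo tablets could be swapped between bottles unnoticed.* That arm does take one of each per dose ("80 mg BID group: 2 tablets AM (1 placebo + 1 active 80 mg) and 2 tablets PM"), but the protocol does not say that they are packed separately.

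**Conclusion.** The definition should be corrected. Two parts of the finding need no assumption about pack size: the score cannot exceed 100%, so the upper limit is void; and the 80% band and the 75% trigger stand on different bases. A third part assumes only a cumulative count: even with no spare tablets, fully adherent subjects score below 80% if they leave before about Day 22, or between the Week 4 supply and about Day 45. Any spare lengthens those windows. Failure of a perfect completer is conditional on more than 25% spare.

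At the planned 15% dropout, 0.15 × 69 ≈ 10 subjects per arm would leave early. The documents do not show how many would fall in the affected windows.

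The effect on results is conditional. The primary analysis does not change. The supportive per-protocol analysis changes only if the band is used to identify violations, which the protocol neither states nor rules out. In that case the misclassification would follow early withdrawal and hence outcome.

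**What to change.** In Section 11.6, and in the SAP, replace the definition with:

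Compliance (%) = 100 × (tablets dispensed − tablets returned) / (4 × days from first dose to the scheduled end of treatment or documented IP discontinuation, whichever comes first).

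Keep the 80-120% band. Reconcile the base of the 75% trigger with this one. State in Section 13.2 or the SAP whether compliance enters the per-protocol definition, before that population is determined.

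The denominator should run to documented discontinuation, not to the last day on which tablets were taken. Otherwise a subject who silently stops on Day 14 of a 28-day period but stays in the study scores 56/56 = 100%, when 56/112 = 50% is the true figure. Because a whole-treatment score can still miss over-use when spare is 20% or less, the visit-by-visit counts in Table 1 should remain in use alongside it.

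The cost is a one-sentence protocol and SAP change and minor programming. Tablet counts and dosing dates are already collected, and the primary mITT analysis is untouched.

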12 CONCOMITANT MEDICATIONS AND PROCEDURES

All medications (prescription and non-prescription), treatments, and therapies taken by the subject from screening throughout their entire participation in the study, including those initiated prior to the start of the study, must be recorded on the subject's source document and on the appropriate page of the eCRF. The dose, unit, frequency, route, indication, date the medication was started, and date the medication was stopped (if not ongoing) must be recorded.

12.1 Prohibited Concomitant Medications and Procedures

The following concomitant medications are prohibited during the treatment portion of the study, Week 0 Visit (Day 1) to the Week 8 Visit, or the Early Termination Visit for subjects who discontinue prematurely during the study:

- Use of any biologic agents, including TNF blockers
- Use of oral aminosalicylates (sulfasalazine [SSZ] or 5-ASA compounds)
- Use of mycophenolic acid, tacrolimus, sirolimus, cyclosporine, or thalidomide
- Use of topical treatment with 5-ASA or corticosteroid enemas or suppositories is prohibited during the study and must be discontinued 2 weeks prior to the Screening Visit
- Use of oral and/or IV corticosteroids is prohibited during the study and must be discontinued 2 weeks prior to the Screening Visit
- Use of AZA, 6-MP, or MTX is prohibited during the study and must be discontinued 8 weeks prior to the Screening Visit
- Chronic use of nonsteroidal anti-inflammatory drugs (NSAIDs).

13 STATISTICAL ANALYSES

13.1 Overview

Key elements of the SAP are outlined in this section. The comprehensive plan will be documented in a separate SAP.

13.2 Study Population Definitions

Safety analyses will be based on the safety population, which will include all subjects who are randomized and receive at least 1 dose of IP. Subjects will be included in the treatment group corresponding to the IP they actually received for the analyses using the safety population.

The ITT population will consist of all subjects who are randomized as specified in the protocol and receive at least 1 dose of IP. Subjects will be included in the treatment group to which they were randomized, irrespective of the treatment actually received, for the analyses using the ITT population.

The modified intent-to treat (mITT) population is defined as the ITT population with the exclusion of the subjects who: a) withdraw from the study due to a reason clearly documented as independent of either the study treatment or the UC; or b) remained on study for less than 7 days. The mITT population will be the primary population for efficacy analyses.

The PP population will consist of all subjects included in the mITT population who have at least 1 post-baseline efficacy evaluation and no protocol violations that may substantially affect the efficacy results. The final determination on these protocol violations, and thereby the composition of the PP population, will be made prior to the Placebo-controlled Phase analysis and will be separately documented.

The PK population will consist of all subjects in the safety population who have at least one analyzable PK sample. It is expected that the PK population will consist of approximately 50% of the overall study population.

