9.11 Early Termination Visit

The Early Termination Visit is based on the subject's withdrawal from the study prior to Week 8. Participation in the study is completely voluntary. Subjects are also free to withdraw from the study at any time if they feel they are not benefiting from the study in order to receive rescue therapy and/or receive treatment with standard medical care. In addition, the Investigator may discontinue the subject from the study at any time based on his/her assessment of clinical efficacy and/or safety. The decision to discontinue a subject remains the responsibility of the treating physician, which will not be delayed or refused by the sponsor. When a subject withdraws or is discontinued from the study, every effort should be made to complete as many safety and efficacy assessments as reasonably appropriate. Refer to Table 1 for the assessments to be performed at the Early Termination Visit.

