13.3 Sample Size and Power Considerations

Given that the purpose of this Phase 2a trial is to determine whether the drug is efficacious and therefore whether to proceed with further development, there is only 1 outcome of interest: superiority of 1 or more experimental arms to the control. In this scenario, a one-sided testing framework is appropriate.

Moreover, given the need for the trial to be small (one or more Phase 3 trials will be required to confirm the efficacy), standard type I error rate control at the 2.5% level is not strictly necessary. For decisions concerning the future of the project, the sponsor will consider a more relaxed approach to false positive rate, allowing a 5% type I error for the one-sided test of the null hypothesis (ie, the primary outcome is no different between each treatment group and control) rather than the usual 2.5% required for a pivotal trial. The use of this higher type I error and of a low type II error of 15% give to the trial a high statistical power to detect the clinically meaningful effects while maintaining an acceptable and feasible size. Finally, because this trial is

a multiple-experimental arm randomized trial with a control, sample size is increased in order to maintain an overall type I error rate as close as possible to the nominal value of 5%. Assuming the following:

- A 6% Clinical Remission rate for the placebo, which after allowing for a 15% dropout rate being interpreted as treatment failure, equates to a 5.1% Clinical Remission rate.
- A 26% Clinical Remission rate for the highest dose of GED-0507-34-Levo (20% more than placebo group), which after allowing for a 15% dropout rate being interpreted as treatment failure, equates to a 22.1% Clinical Remission rate.
- A type I (α) error of 0.05.
- A power of 85%, type II (β) error = 0.15, to detect, if it exists, the above stated difference between GED-0507-34-Levo and placebo.
- A one-tailed test for proportions.
- A drop-out rate of 15%.

Fifty five (55) subjects per group are needed.

However, in order to take into account the multiplicity of the tests and the need of maintaining the experiment-wise error at the nominal alpha level, the number of subjects per group is increased to 69, for a total of 207 subjects. With this number of subjects, the alpha level actually considered is 2.5%, as the Bonferroni-Holm method will require for the significance testing of the lower p-value.

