13.4 Statistical Methods

The primary efficacy variable is the proportion of subjects who are in Clinical Remission at Week 8, as defined by an MMS of ≤ 2 , with individual sub-scores (SF and Endoscopy) ≤ 1 , and RBS = 0.

GED-0507-34-Levo treatment arms will be compared with placebo using the chi-squared test and using the Bonferroni-Holm method to control the false positive error rate. Corresponding confidence intervals for the risk ratios of GED-0507-34-Levo against placebo will be presented. Subjects who withdraw will be assumed not to be in remission at Week 8. The last-observation-carried-forward (LOCF) method will be used to impute MMS in the case of missing values in subjects completing the study. The above primary analysis does not adjust for the effects of center under the assumption that there will be many centers who do not recruit at least 1 subject on every treatment. Should this assumption not appear to be the case, the primary analysis methodology will be updated in the SAP prior to breaking the blind for the study.

The primary analysis of the primary efficacy variable will be on the mITT population and will be the comparison of each of the GED-0507-34-Levo doses against placebo as described above.

Additional supportive analysis of the primary efficacy variable will be performed on the ITT and PP populations. A further exploratory log-binomial regression analysis will be performed to investigate the association of prognostic factors with proportion of subjects in Clinical Remission at Week 8.

Summary statistics will be presented for efficacy variables and their changes from baseline at each time point on the mITT, ITT, and PP populations.

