13.6 Efficacy Analysis

The mITT population (Section 13.2) will be the primary population for efficacy analyses. Supportive analyses using the ITT and PP populations will also be performed for the primary efficacy endpoint.

The primary efficacy variable is the proportion of subjects achieving a clinical remission in the MMS at Week 8, defined as a MMS of ≤ 2 with individual sub-scores (SF and Endoscopy) ≤ 1 , and RBS = 0.

The methodology for the primary efficacy analysis is described in Section 13.4. The following secondary and exploratory efficacy endpoints will be analyzed using similar methodology.

- The proportion of subjects achieving clinical response at Week 8, defined as a decrease from baseline in the MMS of at least 2 points and at least 25 %, along with a reduction in the RBS of at least 1 point or an absolute RBS of ≤ 1
- The proportion of subjects achieving endoscopic remission at Week 8, defined as a Mayo endoscopic sub-score of 0
- The proportion of subjects achieving endoscopic response at Week 8, defined as a decrease from baseline of at least 1 point in the Mayo endoscopic sub-score
- The proportion of subjects achieving a RBS \leq 1 at Week 8

Additional endpoints may be added to the hierarchy and specified in the SAP.

Summary of all efficacy endpoints over time will be provided using frequency and percentage for categorical endpoints and descriptive statistics for continuous endpoints.

The MMS consists of the SFS, RBS, and endoscopy sub-scores of the TMS and excludes the PGA sub-score, since this is a global measure that is subjective in nature. Each of these parameters will be assessed on a scale of 0 to 3. The sum of scores for all 3 parameters will determine the MMS. The MMS ranges from 0 to 9 points.

Clinical response is defined as a decrease from baseline in MMS of at least 2 points and at least 25%, with an accompanying decrease in the RBS of at least 1 point or an absolute RBS of 0 or 1. Assessment of sigmoidoscopic appearance will be performed in the worst inflamed area in the rectum or in the sigmoid if the rectum is not inflamed. The same area should be evaluated at baseline and at the End of Study/Early Withdrawal Visit.

Images of all endoscopic procedures will be captured and sent to a centralized reader for their assessment.

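### The primary (mITT) population drops randomised, dosed subjects for post-randomisation events, including anyone on study under 7 days for any reason, while the sample size counts every dropout as a failure

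*Combined protocol and SAP*

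**What the plan says.** Section 13.2 defines ITT as every randomised subject who took at least one dose. The mITT set removes from ITT those who (a) "withdraw from the study due to a reason clearly documented as independent of either the study treatment or the UC", or who "b) remained on study for less than 7 days. The mITT population will be the primary population for efficacy analyses". Clause (a) depends on the reason for leaving; clause (b) does not.

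Section 13.4 repeats the choice: "The primary analysis of the primary efficacy variable will be on the mITT population". Section 13.6 also names mITT as primary and adds: "Supportive analyses using the ITT and PP populations will also be performed for the primary efficacy endpoint".

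Section 13.4 treats withdrawals as failures: "Subjects who withdraw will be assumed not to be in remission at Week 8". Section 13.3 sizes the trial on remission rates reduced for a "15% dropout rate being interpreted as treatment failure", which takes 6% to 5.1% on placebo and 26% to 22.1% on active.

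Section 9.11 states that "the Investigator may discontinue the subject from the study at any time based on his/her assessment of clinical efficacy and/or safety".

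**The concern.** Both exclusions act on events after randomisation and dosing. Because Section 9.11 permits discontinuation for efficacy or safety at any time, a departure before day 7 can be caused by the drug or by the disease. Clause (b) then deletes that subject from the primary denominator. The non-remission rule in Section 13.4 can be read as applying within mITT, but it cannot reach a subject who has already been removed.

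Clause (a) is narrower but needs a judgement about cause. Section 13.2 says when the protocol violations that define the PP set will be settled; it says nothing comparable about when, or by whom, reasons under clause (a) are classified.

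A withdrawn subject would otherwise count as a non-remitter, so each exclusion can only raise the observed remission rate of that subject's arm (or leave it at zero). If the arms lose different numbers, the primary comparison is biased: more exclusions on active favour the drug, and more on placebo work against it. Different early losses are plausible, though not shown. Section 5.3 reports related adverse events leading to permanent discontinuation in the earlier Phase 2a study, and Section 5.5 says this trial uses a new formulation and adds a doubled daily dose.

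**Working it through.** **1. Reproduce the planned sample size.** Inputs from Section 13.3: p0 = 0.06 × 0.85 = 0.051; p1 = 0.26 × 0.85 = 0.221; power 85%; one-sided alpha 0.05, then 0.025 for the smaller p-value under Bonferroni-Holm. The formula is the normal approximation with unpooled variance:

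n = (z(1−alpha) + z(0.85))² × [p0(1−p0) + p1(1−p1)] / (p1−p0)²

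The variance term is 0.051×0.949 + 0.221×0.779 = 0.2206, and the squared difference is 0.17² = 0.0289.

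- Alpha 0.05: 7.189 × 0.2206 / 0.0289 = 54.9, so 55 per arm, as stated.
- Alpha 0.025: 8.978 × 0.2206 / 0.0289 = 68.5, so 69 per arm, as stated. Power at n=69 is 85.2%.
- The same formula with all rates × 0.85 and n=69 gives 89.2, 87.2, 85.2, 83.3, 81.4, 79.6 and 77.9%, which match all seven rows of Table 2.
- With undiluted rates (6% v 26%) it gives 56 at alpha 0.025, or 66 after dividing by 0.85. Neither is 69.

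So with this formula the stated figures reproduce only when all dropouts stay in the denominator as failures. That is the ITT rule, not the mITT rule.

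**2. Effect of exclusions at the planned rates.** The documents give no exclusion counts. I assume 0 to 10 per arm (15% of 69 is about 10), with every excluded subject a non-remitter. Removing k subjects from an arm changes its rate from p to p × 69/(69−k).

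| Placebo removed | Active removed | Risk ratio | Power (one-sided 0.025) |
|---|---|---|---|
| 0 | 0 | 4.33 | 85.2% |
| 4 | 4 | 4.33 | 85.7% |
| 10 | 10 | 4.33 | 86.6% |
| 0 | 2 | 4.46 | 86.5% |
| 0 | 5 | 4.67 | 88.3% |
| 0 | 10 | 5.07 | 91.0% |
| 5 | 0 | 4.02 | 82.3% |
| 10 | 0 | 3.71 | 78.5% |

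In the active-only rows the higher figure is not a gain. It comes from the inflated active rate.

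**3. Can the verdict change?** One-sided p-values from the chi-squared test (pooled variance, no continuity correction), compared with 0.025:

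- 4/69 placebo v 11/69 active: p=0.028, not significant. Remove 2 active non-remitters (11/67): p=0.024, significant.
- Remove 4 from each arm instead (4/65 v 11/65): p=0.027, no change of verdict.
- 3/69 v 10/69: p=0.021, significant. Remove 4 placebo non-remitters (3/65): p=0.027, not significant.

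**4. Type I error.** Full binomial enumeration for one dose against placebo, 69 randomised per arm, the same true remission rate in both arms, one-sided 0.025:

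| Excluded | True rate 5.1% | True rate 10% |
|---|---|---|
| none | 2.39% | 2.55% |
| 5 active only | 3.18% | 3.41% |
| 10 active only | 4.03% | 5.14% |
| 10 placebo only | 1.43% | 1.26% |

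**The case against.** The strongest reply is that the practical effect is probably small.

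- **Balanced exclusions do no harm.** This stands. The mismatch with the sample size does not by itself cost power.
- **The large scenarios are extreme.** Ten exclusions on active and none on placebo would need every expected active dropout to meet an exclusion. Section 5.5 says that many subjects left the earlier study for no effect or worsening within 4 weeks. Such subjects would stay in mITT as failures unless they left before day 7. This stands: the 10-subject rows are outer bounds.
- **The reversals are boundary cases.** Enumeration shows that removing 2 active non-remitters changes the verdict with probability of about 2% at the planned rates, and under 1% when there is no effect. Also, 0.025 applies only to the smaller p-value; if that is rejected, Holm tests the other dose at 0.05. This stands too.
- **The 7-day limit has a rationale.** Table 1 places the first post-baseline visit at Day 7, so clause (b) broadly removes subjects with no scheduled post-baseline assessment. That does not justify removal, because Section 13.4 needs no assessment to classify a withdrawal as a non-remitter.
- **Blinding protects the judgement.** It reduces the risk under clause (a). It does not prevent real differences between arms in early tolerability or worsening, and clause (b) involves no judgement.
- **ITT is already supportive, and disposition is tabulated.** A discrepancy would be visible, and Section 13.3 expects Phase 3 confirmation. But the plan has no rule for an mITT result and an ITT result that disagree, and the primary result is the mITT one.

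**Conclusion.** The concern holds and should be fixed. On the text it is clear: clause (b) removes early failures whatever the reason, three sections make that set primary, and the 69 per arm rests on a different rule. The size is uncertain because it depends on exclusion counts that the documents do not give, and the direction depends on which arm loses more subjects. With equal losses the effect is negligible. If 5 active and no placebo subjects are excluded, the one-sided error for a single comparison is 3.2-3.4% instead of 2.4-2.6%; 10 active-only exclusions give an outer bound of 4.0-5.1%. These figures assume that all excluded subjects are non-remitters and that the common true remission rate is between 5.1% and 10%. Section 13.3 already relaxes the overall one-sided error to 5%, so there is little reason to accept a further, avoidable source of inflation.

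**What to change.** In Sections 13.2, 13.4 and 13.6, name ITT as the primary efficacy population and make mITT and PP supportive. Suggested wording: *The primary efficacy analysis uses the ITT population, analysed by randomised arm; mITT and PP analyses are supportive.* Keep the Section 13.4 rule on withdrawals, so that it covers every withdrawal in the primary analysis. The separate SAP announced in Section 13.1 should carry the same wording.

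The cost is wording in three sections. The ITT analysis is already planned, and 69 per arm with 85% power already assumes that dropouts are failures, so neither changes. The observed remission rates will be slightly lower than under mITT: at the planned active rate, 22.1% instead of 22.8% (22.1 × 69/67) if 2 subjects would have been excluded, or instead of 25.8% (22.1 × 69/59) if 10.
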